## 1. BACKGROUND

This Morbidity and Mortality Statistical Analysis Plan (SAP) supplement accompanies the main Statistical Analysis Plan (360050-001). Where applicable, the analyses defined in this Morbidity and Mortality SAP supplement supersedes the main SAP and the current Bayesian Adaptive Design Report (BADR). In particular; this SAP supplement describes the data analyses planned to demonstrate device benefit for the morbidity and mortality endpoint to support the M&M supplemental PMA (PMA-S) Submission.

After evaluating the pre-planned Expedited Phase data as defined in the main SAP, a large, important and clinically relevant population emerged. This population subgroup is characterized by having an NT-proBNP < 1600 pg/ml. This subgroup is the focus of this SAP supplement.

The M&M analyses will support a PMA-S submission for the following Indication for Use statement: The BAROSTIM NEO System is indicated for patients with heart failure. Heart failure is defined as: New York Heart Association (NYHA) functional Class III or Class II (who had a recent history of Class III), a left ventricular ejection fraction (LVEF)  $\leq$  35% and a NT-proBNP < 1600 pg/ml despite being treated with the appropriate heart failure guideline-directed medical therapy, excluding subjects eligible for Cardiac Resynchronization Therapy (CRT) according to AHA/ACC/ESC guidelines.

In Table 1 below, data that has already been analyzed (data as of 03OCT2018) in the Interim Data for the respective endpoint is called *interim data*. The prospective confirmatory data, which has yet to be accrued and/or analyzed for the respective endpoint, is called the *prospective data*. The **Subgroup** refers to subjects with a baseline NT-proBNP < 1600 pg/ml. This SAP describes the plans for analyzing the Final M&M data to support the M&M PMA-S Submission (last column in Table 1 below).

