  - If COVID-19 is not the primary reason for hospitalization, the committee indicates whether it was a contributing factor.
  - If a determination cannot be made regarding the primary reason, the committee marks both as the primary reason.

Despite, or possibly because of, these changes, the impact of COVID-19 on the overall Barostim Therapy (BAT) treatment effect in this trial is unknown. Therefore, the following approach has been outlined to evaluate and measure any potential impact on the M&M endpoint. Sixty percent (60%) of the approximate 320 expected primary events occurred prior

to March 13, 2020. Thus, approximately 40% of the expected events will accrue during the COVID pandemic. This section outlines additional analyses of the M&M endpoints that may be conducted, as well as the qualitative summaries that will be provided in the assessment of the impact of the COVID-19 pandemic on the M&M data and conclusions.

To evaluate the impact of COVID-19 on the morbidity and mortality endpoints, an indicator variable reflecting events pre vs post the March 13, 2020 date will be included in the regression model and evaluated using a treatment-by-COVID-19 interaction. A p-value less than 0.15 for the interaction term will be considered evidence of a significant interaction between the treatment effect pre COVID-19 vs post COVID-19 (consistent with the interaction p-value for site and gender defined in the main Statistical Analysis Plan 360050-001). However, an insignificant interaction p-value ( $p \geq 0.15$ ) does not necessarily mean that there is no significant difference in the magnitude of the benefit from Barostim therapy pre vs post COVID-19, primarily due to potentially low statistical power for evaluating the interaction term. Thus, the interaction p-value will be included as part of the totality of information used to characterize and evaluate the potential impact of COVID-19.

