A stratified analysis, using the negative binomial model as specified in the primary analysis, may also be performed to further evaluate any difference in treatment effect pre-March 13, 2020, versus post-March 13, 2020. Separate estimates of the treatment effect will be made with data pre-March 13, 2020, and post-March 13, 2020. The follow-up time for the first model will be censored on March 12, 2020, while the follow-up start time for the second model will be March 13, 2020. The Anderson-Gill method for recurrent events model may also be used along with a time-varying covariate for follow-up pre- and post- March 13, 2020. The significance of the time-varying covariate as well as the interaction with treatment group would be reported. As with the negative binomial model, a p-value for the interaction term less than 0.15 will be considered evidence of a significant interaction between the treatment effect pre COVID-19 vs post COVID-19.

If there is evidence that the treatment effect is different pre- vs post-March 13, 2020, then the benefit observed pre-March 13, 2020 would be more consistent with the assumptions and definitions of the study endpoints. This includes the definition and assumed event rate for heart failure hospitalization, as it has been observed that patients have shown a reluctance to interact with the health care setting during the COVID-19 pandemic, some by reducing their risk of hospitalization by changing their behaviors and others by receiving care remotely to replace what may have previously been a hospitalization (e.g. acute medication changes).

In addition to the analyses specified above, other additional relevant information will be considered, such as:

- Number and percent of pre- vs post- March 2020 information (events, follow-up time, rate)
- Follow-up visit compliance pre- vs post- March 2020
- Comparison of other definitions of heart failure on event rates between treatment arms pre- vs post- March 2020, such as
  - Expanded definition of heart failure (see CEC Charter)
  - Unscheduled clinic visits

- Acute changes in medications
- Evaluate the impact using the responses on the COVID-19 case report form. This includes summarizing, or incorporating in the analyses, the instances where subjects reported the need to go to an emergency department or hospital for their heart failure but decided not to because of concerns about COVID-19.

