- Evaluate the information regarding the CEC determined impact of COVID-19 on events, such as HF hospitalizations where CEC determined the event was a study endpoint, but COVID-19 was considered a “Co-primary” or a contributing factor, or where COVID-19 was the primary reason for hospitalization, but heart failure was the secondary reason.
- Evaluate all COVID related adverse events and deaths
- Evaluate COVID related deviation and the impact on the trial and results

There are three interim analyses schedule at approximately 140 (44%, Jan 2020), 180 (~56%, Oct 2020), 240 (~75%, Oct 2021) primary endpoint events, and a final at ~320 events (100%, TBD). Thus, the first and possibly much of the second interim analyses primarily include data that were not impacted by COVID-19. As such, these analyses may also provide insight into the impact of COVID-19 and will be provided in the PMA Supplement submission.

The totality of evidence available will be considered when evaluating the impact of COVID. This includes all evidence of a differential treatment effect of Barostim therapy pre- vs. post-March 13. This includes, at a minimum, the analyses specified above as well as the qualitative assessments of the impact of the COVID-19 pandemic on the study based on the relevant information collected above.

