## 8. ASSUMPTIONS FOR THE PRIMARY MORBIDITY AND MORTALITY ENDPOINT

### 8.1. Power and Type I Error Calculation

Since a subgroup of patients with partial data has been previously analyzed, the relevant power and type I error for the future interim analyses is the conditional power and type I error, accounting for the fact that partial data has been previously analyzed. That previous analysis did not incur any alpha spending since there were no criteria for stopping the trial for success based on that analysis.

The conditional power and type I error are calculated by Monte Carlo methods using simulations of hypothetical trial data simulated according to the joint negative binomial model with parameters estimated based on the trial data through 03October2018.

Prospective follow-up and events from 03OCT2018 through trial completion at 320 events are simulated using a negative binomial model. Multiple hypothetical sets of future events are simulated and the pooled data, including observed and simulated data, is analyzed using the joint negative binomial model.

Pooling the data is equivalent to 100% borrowing. Pooling is performed in order to maintain the interpretability of the analysis, due to the intractability of separating the cumulative follow-up data into separate time periods while maintaining interpretability. The impact of 100% borrowing on type 1 error is accounted for by using a sufficiently rigorous nominal alpha such that conditional type 1 error is well controlled at less than 5%.

Programs will be provided to FDA that implement the Monte Carlo calculations.

Using 20,000 simulations for the null and 1000 simulations for the alternative under the assumptions below, the conditional power is 86.0% and the type I error is 4.4% when using an alpha spending function with a cumulative alpha level of 0.01. The stricter alpha level is sufficient to offset the tendency of the interim data to inflate the type 1 error. Using a group sequential spending function with a cumulative alpha of 0.01 results in controlling the type 1 error to less than 5% across a range of scenarios.

The base case uses the following assumptions for the conditional power and type I error calculations:

1. Control arm event rate of 0.4 events per patient year
2. Power calculated assuming an expected relative reduction in the endpoint event rate of  $1 - \exp(\beta_1) = 0.35$

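### The pre/post-COVID comparison puts all of the already analyzed, device-favouring data through 03OCT2018 in the pre-COVID period, so if the true benefit is near zero a pre/post difference can appear without any COVID effect.

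*SAP*

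**What the plan says.** The primary analysis pools new and previously analyzed follow-up and events (SAP Section 3.1.5). Data as of 03OCT2018 had already been analyzed, and it was after evaluating the Expedited Phase data that "a large, important and clinically relevant population emerged" (Section 1), namely subjects with NT-proBNP below 1600 pg/ml.

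Section 8.1 acknowledges that these early data lean toward the device. Of the cumulative alpha of 0.01 it says: "The stricter alpha level is sufficient to offset the tendency of the interim data to inflate the type 1 error". Table 5 gives the resulting conditional type I error in the base case as 0.0436.

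Section 7 adds a treatment-by-COVID interaction, with p<0.15 as evidence of a difference, and optional separate models for the two periods. For the pre-COVID model, "The follow-up time for the first model will be censored on March 12, 2020"; no start date is given. A recurrent-event version is also optional: "The Anderson-Gill method for recurrent events model may also be used along with a time-varying covariate". If the periods differ, "the benefit observed pre-March 13, 2020 would be more consistent with the assumptions and definitions of the study endpoints", and the explanation offered is changed care-seeking. Section 7 also presents the 140- and 180-event looks as possible insight into COVID; both contain the early data. It describes the interaction as supporting evidence: "the interaction p-value will be included as part of the totality of information used to characterize and evaluate the potential impact of COVID-19".

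**The concern.** The data through 03OCT2018 fall wholly in the pre-COVID period and not at all in the later one. They are known to favour the device. If the true benefit is smaller than they suggest, later data will regress toward the truth, and the pre-COVID period will look better for a reason unrelated to the pandemic. The SAP allows for this lean in the primary test through the stricter alpha. Section 7 has no counterpart for the interaction, the period-specific estimates or the recurrent-event model, and does not mention regression to the mean.

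At stake is how a missed primary endpoint, or a weak late effect, is explained in the PMA supplement. The case that matters most is a true effect near zero, where a COVID explanation would mislead most and where the artefact is largest.

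**Working it through.** **Inputs.** Hwang-Shih-DeCani spending, gamma = -3, cumulative alpha 0.01 (Sections 3.1.3 and 8.1). Alpha spent at the looks is 0.0019, 0.0011, 0.0024 and 0.0046, with Z-boundaries 2.9032, 2.8781, 2.6713 and 2.4335 (Table 7). Conditional type I error is 0.0436 and power at rate ratio (RR) 0.65 is 0.860 (Table 8). The documents do not give the October 2018 Z-value, its information share or its event count, so these are inferred. I take p<0.15 as two-sided, i.e. 7.5% in each direction (critical value 1.44).

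**1. Information at the looks.** The spending function is alpha(t) = 0.01 (e^{3t} - 1)/(e^3 - 1). Cumulative spend of 0.0019, 0.0030 and 0.0054 gives t = 0.511, 0.635 and 0.808, with 1 at the final look.

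**2. Reproducing the plan.** Boundaries recomputed at these fractions are 2.894, 2.879, 2.671 and 2.433, close to Table 7.

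**3. Inferring the October 2018 result.** For information shares t0 of 0.14 to 0.26, matching 0.0436 and 0.860 requires z0 of 1.86 down to 1.66 and a final standard error (SE) of 0.139 down to 0.130. A central fit is t0 = 0.20, z0 = 1.7, SE about 0.1345, which implies an October 2018 RR of exp(-1.7 x 0.1345/√0.20) = 0.60. Figures not used in the fit agree:
- Minimum observed reduction: 1 - exp(-2.4335 x 0.1345) = 27.9% (Table 2: 28%).
- Power in the row labelled 45%: 0.986 (Table 8: 0.985).
- Power in the row labelled 25%, taken as RR 0.75: 0.556 (Table 8: 0.553).

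**4. Pre-COVID information share tp.** Section 7 says: "Sixty percent (60%) of the approximate 320 expected primary events occurred prior" to 13 March 2020. That is 192 events, so tp = 0.635 + (12/60)(0.808 - 0.635) = 0.67. The look dates in the same section, "140 (44%, Jan 2020), 180 (~56%, Oct 2020), 240 (~75%, Oct 2021) primary endpoint events", suggest less if read as event dates. 13 March is about two of the nine months from the 140- to the 180-event look, so tp is about 0.511 + (2/9)(0.124) = 0.54. The 60% statement is the more direct; 0.54 is used as the lower end.

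**5. The contrast, with no COVID effect.** With drift δ = -ln(RR)/SE, the contrast given the October 2018 data has:
- mean (z0√t0 - δ t0)/tp
- variance (tp - t0)/tp² + 1/(1 - tp)
- flag threshold 1.44 √[1/tp + 1/(1 - tp)]

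At t0 = 0.20, tp = 0.67 and RR 1:
- mean = 1.7 x √0.20/0.67 = 0.760/0.67 = 1.13
- SD = √(0.47/0.449 + 1/0.33) = 2.02
- threshold = 1.44 x 2.127 = 3.06
- P(flag favouring pre-COVID) = 1 - Φ((3.06 - 1.13)/2.02) = 17%

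The mean is zero when the true effect equals the October 2018 estimate, which is why the distortion fades as the benefit grows.

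| True RR in both periods | Mean of contrast (t0 = 0.20) | Flag rate (t0 = 0.20) | Flag rate, t0 0.14-0.26 |
|---|---|---|---|
| 1.00 | 1.13 | 17% | 16-18% |
| 0.90 | 0.90 | 14% | 14% |
| 0.75 | 0.50 | 10% | 9-12% |
| 0.65 | 0.18 | 8% | 6-10% |

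At tp = 0.54 and RR 1 the range is 20-23%. Among trials that miss the primary at all four looks, the no-effect rate at tp = 0.67 is again 16-18%.

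**6. Starting the pre-COVID period after 03OCT2018.** The remaining increments are independent of the October 2018 result, so the rate returns to 7.5% at every RR.

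**7. Patient-level check.** A gamma-frailty negative binomial simulation at no effect used rate 0.4, shape 1.7, terminal fraction 0.18 and assumed enrolment timing. It flagged the pre-COVID period in 14.5-16% of trials with the early data included and about 6% without them. About 6% was also the rate when nothing was conditioned on the October 2018 result.

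**8. Power for a real COVID effect.** These are chances of a flag favouring the pre-COVID period after a missed primary, for t0 0.14-0.26 and tp 0.54-0.67.

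| RR before, then after | Planned contrast | Contrast without the early data |
|---|---|---|
| 0.65, then 1.0 | 49-57% | 33-38% |
| 0.75, then 1.0 | 37-46% | 23-25% |

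Part of the gap in the second row is the early lean itself.

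**The case against.** No decision rests on this contrast. Success is the group sequential boundary (Section 3.1.4), the separate-period and recurrent-event models are optional, and the interaction is one item beside the COVID case report form, the event committee's attribution and visit compliance. The lean of the early data is disclosed in Sections 8.1 and 8.3, and the programs go to FDA. At the better-supported share, more than 80% of no-effect trials would not be flagged. All of this stands and limits the point to interpretation. None of it removes the early data from the contrast or tells the reader that they could produce the difference.

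Section 8.1 justifies pooling by the difficulty of separating follow-up into periods. Section 7 already separates it at 13 March 2020, so one more cut date is no harder in kind.

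The objection about power also stands. The contrast without the early data loses real power, and after a miss with no COVID effect it flags below nominal: about 7% at no effect and 3-4% at RR 0.65. It should not replace the planned contrast.

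A reader might infer more than the documents support:
- That the SAP treats the pre-COVID estimate as unbiased, or would let it stand in for the primary result. The sentence in Section 7 concerns consistency with the assumed event definitions and rates, and Section 3.2 leaves the primary analysis unchanged.
- That morbidity and mortality results drove the choice of subgroup. The documents do not show this, and the mechanism needs only that the early data lean toward the device.

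**Conclusion.** The point holds as a limited matter of interpretation. With a true benefit near zero and no COVID effect, the planned interaction favours the pre-COVID period about 2.1 to 2.4 times as often as its nominal 7.5% (16-18%), and up to about 3 times as often (23%) if the pre-COVID information share is as low as 0.54. The excess is smaller at RR 0.90 (about 14%) and largely gone by RR 0.65.

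The direction follows from the SAP's own statement about type I error. The size rests on an October 2018 Z-value and information share inferred from Tables 7 and 8, on an assumed pre-COVID share, and on a correctly calibrated interaction test. Confidence in the exact figures is therefore medium.

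**What to change.** In the supportive COVID analyses of SAP Section 7:
- Report the treatment effect for three periods: through 03OCT2018, 04OCT2018 to 12MAR2020, and 13MAR2020 onward.
- Show the treatment-by-COVID contrast on the last two periods, with a standard error robust to within-subject correlation, beside the planned two-period contrast.
- Add to the sentence on the pre-March 2020 benefit that a pre/post difference may also reflect the favourable early data, so a COVID attribution should be read from both contrasts and not from the two-period contrast alone.
- Do not make the added contrast decisive.

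The cost is SAP wording and one extra cut date, with no new data and no change to the primary analysis. The added contrast is less precise: at t0 = 0.20 and tp = 0.67 its standard error on the log scale is 0.1345 x √(1/0.47 + 1/0.33) = 0.31, against 0.1345 x 2.127 = 0.29 for the planned one. Its lower power for a real COVID effect should be stated where it is reported. Some within-subject carry-over remains, because up to 241 subjects randomized before the October 2018 cut continue in follow-up (Table 2). In simulation it affected the last two periods about equally (no-effect RR 0.95-0.96 and 0.96-0.97).

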## 8. ASSUMPTIONS FOR THE PRIMARY MORBIDITY AND MORTALITY ENDPOINT

### 8.1. Power and Type I Error Calculation

Since a subgroup of patients with partial data has been previously analyzed, the relevant power and type I error for the future interim analyses is the conditional power and type I error, accounting for the fact that partial data has been previously analyzed. That previous analysis did not incur any alpha spending since there were no criteria for stopping the trial for success based on that analysis.

The conditional power and type I error are calculated by Monte Carlo methods using simulations of hypothetical trial data simulated according to the joint negative binomial model with parameters estimated based on the trial data through 03October2018.

Prospective follow-up and events from 03OCT2018 through trial completion at 320 events are simulated using a negative binomial model. Multiple hypothetical sets of future events are simulated and the pooled data, including observed and simulated data, is analyzed using the joint negative binomial model.

Pooling the data is equivalent to 100% borrowing. Pooling is performed in order to maintain the interpretability of the analysis, due to the intractability of separating the cumulative follow-up data into separate time periods while maintaining interpretability. The impact of 100% borrowing on type 1 error is accounted for by using a sufficiently rigorous nominal alpha such that conditional type 1 error is well controlled at less than 5%.

Programs will be provided to FDA that implement the Monte Carlo calculations.

Using 20,000 simulations for the null and 1000 simulations for the alternative under the assumptions below, the conditional power is 86.0% and the type I error is 4.4% when using an alpha spending function with a cumulative alpha level of 0.01. The stricter alpha level is sufficient to offset the tendency of the interim data to inflate the type 1 error. Using a group sequential spending function with a cumulative alpha of 0.01 results in controlling the type 1 error to less than 5% across a range of scenarios.

The base case uses the following assumptions for the conditional power and type I error calculations:

1. Control arm event rate of 0.4 events per patient year
2. Power calculated assuming an expected relative reduction in the endpoint event rate of  $1 - \exp(\beta_1) = 0.35$
3. Type I error calculated assuming an expected relative reduction in the endpoint event rate of  $1 - \exp(\beta_1) = 0$ , equivalent to no treatment effect
4. Statistical significance threshold given by the Hwang-Shih-DeCani spending function with  $\gamma = -3$

5. Sample size of 331 subjects with baseline NT-proBNP < 1600, consisting of 259 subgroup subjects randomized through 03October2018 and an additional 72 subjects to be prospectively randomized.
6. Parameter describing the relationship between events in the year prior to randomization and the expected rate of events during follow-up (beta) of 1.8
7. Parameter describing the probability that an event is a censoring event (p) of 0.18
8. Parameter describing the dispersion of the negative binomial data (alpha) of 1.7

## 8.2. Operating Characteristics

The operating characteristics under the group-sequential evaluation of the morbidity and mortality results are summarized below. In addition to varying the treatment effect assumption under the assumptions of the base case, the power and type 1 error of the trial were also evaluated under a variety of scenarios where other parameters differ from the base case assumptions.

Table 4 shows the variety of scenarios explored under the null effect size to demonstrate that the type 1 error is controlled to less than 5% even if accrual, event rate, censoring probability, and dispersion differ from the data observed as of 03October2018. Compared to the scenarios explored in the original trial design, the variation in parameters is lower due to the previous information observed. The value of beta is not varied since a very high proportion of patients have known data regarding the events in the year prior to enrollment.

